2.2.3 Minimization of Risks

Research participants will be carefully screened to meet enrollment criteria. Participants meeting exclusion criteria will not be enrolled. The study participant informed consent will be presented with clear description of the study requirements and opportunity to have questions answered before enrollment. Once an event occurs review of symptoms will be ascertained at 15 and 30 minutes for up to an hour. Reporting of adverse events will be reviewed routinely and in accordance with regulatory guidelines (21CFR, GCP) by the Principal Investigator. Participants with occurrence of worsening symptoms or adverse events should stop taking the test product and may seek medical attention and exit the study.

3 Study Objectives

Beyond the obvious physical symptoms, lifestyle impact related to tension headaches include decreased work productivity and lost work time [17, 18]. The purpose of the present study is to 1) evaluate the impact of the tension relief test product on the symptoms of tension headaches and functional status in adult men and women who suffer from mild to moderate tension headaches by using the 10-point Mankoski scale [19] and 2) the

subjective experience of these participants related to general health, symptoms of tension headaches, and personal experience with the products.

This will be evaluated based on the primary and secondary endpoints. These endpoints, the analysis populations, and their respective measures are described below. Further details on the methods for measuring the outcomes can be found in the Study Outcome Measures and Analysis Plan sections.

Primary Endpoint:

The primary endpoint is reduction in tension headache severity. Patients will be asked to rate headache on the 10-point Mankoski scale at 4 time points: prior to taking the product, 15 minutes after taking the product, 30 minutes after taking the product and 1 hour after taking the product. The improvement in symptoms from baseline will be evaluated on a pairwise basis separately for each time point. P-values will be computed for the improvement.

There is no control group for the primary analysis.

Secondary Endpoints:

- The time to other intervention will be analyzed.
- A longitudinal analysis will be performed for patients who report on more than one incident of headache.
- Comparison against the participant's normal behavior.
- Net Promoter Score.
- Adverse events will be summarized.

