4.3 Participation Period

Participants are expected to participate in the study for 60 days after study start. The product may be used after each onset of tension headache, but not more often than three times per day. Patients will be discontinued from the study 60 days after study start or after three recorded headache episodes. Study start is defined as the day the participant received the test product and completed the receipt of test product form.

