- After completing the surveys, the participant will take test product. The participant will take 2 capsules with 6-8 oz. of water per headache episode. With a max of 6 pills per day. (If participant takes 6 pills in 1 day this will be defined as 3 headache episodes and the patient will be exited from the study).
- After taking the test product, the participant will complete a Mankoski pain scale at 15 minutes, 30 minutes, and 1 hour after taking the test product.
- Once the participant's symptoms resolve, the participant will complete the headache diary.
- If the participant takes any other medication outside of the test product, the participant will record this on the headache diary.
- After taking the test product, the participant will be instructed to fill out an Adverse Event form for any side-effects experienced.
- After the first headache episode, the participant will be asked to complete the same process for another 2 headache episodes; however, these are not required.
- If the participant completes the required assessments for a total of 3 headache episodes, they will be prompted, by email, to exit the study.

- If the participant only completes the required assessments for the required 1 headache episode, the participant will be prompted, by email, to complete the study exit form and will be exited from the study on day 60 (60 days from the day of receipt of the test product).
- The sponsor nor Hawthorne Effect Inc. will not make any attempt to collect any unused product.
- Upon receipt of study exit survey and review of completed study forms, participant will receive an Amazon gift card of \$25 via email.

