6.4 Adverse Event and Safety Monitoring

Adverse Events (AEs) are defined as any untoward medical occurrences described by the study participant. All AEs will be self-reported and documented on the platform. The AEs will be reviewed by the study team including the remote trial coordinator and study principal investigator and reported according to the IRB requirements. Participants who experience adverse events will be advised to stop taking the test product and seek medical attention.

In the event that a participant experiences an adverse event, the clinical study manager or clinical ops coordinator will notify both the PI and Sponsor. The Sponsor will take appropriate action according to their standard operating procedures for any adverse events that warrant action by the Sponsor.

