7.1 Study Outcomes Measures

Analysis populations:

The *intent to treat* (ITT) population consists of all participants who are consented, report the onset of a headache, and have taken the study medication at least once. The primary analysis will be in the ITT population.

Primary Endpoint:

The primary endpoint is reduction in headache severity. Patients will be asked to rate headache on the 10-point Mankoski scale at 4 time points: prior to taking the product, 15 minutes after taking the product, 30 minutes after taking the product, and 1 hour after taking the product. The improvement in symptoms from baseline will be evaluated on a pairwise basis separately for each time point. P-values will be computed for the improvement.

There is no control group for the primary analysis.

Secondary Endpoints:

- Time to intervention (taking any product other than the study medication) will be analyzed as a time dependent variable, with the clock starting when the test product is taken.
- A longitudinal analysis will be performed for patients who report on more than one incident of headache.
- Net Promoter Score.
- Comparison against normal behavior will use the paired sample *t*-test.
- An additional data presentation will consist of results from both Treatment and Control

in similar studies appearing in the literature. There will be no formal statistical comparison of results from this study and historical studies.

Secondary endpoints will be gathered on the subjective experience of these participants related to general health, personal experience with the product. The secondary endpoints will be self-reported by the participant on their online portal. There will be a questionnaire related to general health and the subjective experience of the participant administered at baseline and at study exit.

The purpose of the secondary analyses is to investigate the association between various baseline and other measurements and outcomes. These secondary analyses are considered hypothesis generating, and the descriptions are somewhat informal. The trial data may suggest secondary analyses not described here.

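### The longitudinal analysis is limited to repeat reporters, a group partly selected on first-episode outcome and on headache frequency; it is likely to overstate improvement and may show a spurious decline across episodes

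*Combined protocol and SAP*

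**What the plan says.** Section 7.1 lists among the secondary endpoints: "A longitudinal analysis will be performed for patients who report on more than one incident of headache". Section 3 and the synopsis carry the same restriction. No model, outcome contrast or handling of single-episode participants is given, and section 7.3 leaves detail to a SAP still to be written.

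Three other provisions decide who enters this group:

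- **Optional repeats.** After the first episode, "the participant will be asked to complete the same process for another 2 headache episodes; however, these are not required" (section 6.1).
- **Stopping advice.** "Participants with occurrence of worsening symptoms or adverse events should stop taking the test product" (section 2.2.3), and "Participants who experience adverse events will be advised to stop taking the test product and seek medical attention" (section 6.4).
- **Time window and cap.** "Patients will be discontinued from the study 60 days after study start or after three recorded headache episodes" (section 4.3). Baseline headache frequency, from a few times a year to daily, is collected in Appendix D.

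The primary analysis uses the ITT population: consented participants who report a headache and "have taken the study medication at least once" (section 7.1). On the secondary analyses, section 7.1 says: "These secondary analyses are considered hypothesis generating, and the descriptions are somewhat informal".

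**The concern.** To be analysed longitudinally, a participant must return for a second, optional dose. A poor first episode is a stated reason not to: section 2.2.3 ties stopping to worsening symptoms, and headache severity is the measured outcome. Repeat reporters are then likely to have had better first episodes than treated participants in general.

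Two distortions follow if re-use rises with first-episode improvement. Mean improvement among repeat reporters exceeds that of all treated participants. And because part of a good first result is chance, their second result falls back toward the mean, which looks like waning benefit even when the true effect is constant.

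Leaving single-use participants out of this analysis removes the first-episode data that would allow a correction. With no control group, nothing else in the study would reveal the problem. The results matter beyond description: the synopsis says they may inform a two-arm trial, and section 10 mentions promotional use.

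**Working it through.** **1. The plan's own figure.** Section 7.2 gives a mean improvement of 2, SD 5, and 68 patients for 90% power with a paired t-test. Alpha is not stated; two-sided 0.05 is assumed. The normal approximation is ((1.960 + 1.282) × 5 / 2)² = 65.7, so 66. The noncentral t gives 68, with power 90.2%. The figure reproduces, with 5 as the SD of the change. The documents give no figure for the longitudinal analysis.

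**2. Formula.** Let improvement have the same true mean μ at both episodes (no real decline) and within-person correlation ρ. Let M1 be the mean first-episode improvement among repeat users. If re-use depends only on first-episode improvement, then:

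- second-episode mean among repeat users: M2 = μ + ρ(M1 − μ)
- false decline: M1 − M2 = (1 − ρ)(M1 − μ)

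**3. Re-use rising with first-episode improvement.** Assumptions, none from the documents: μ = 1.5, between-person SD 1.0 or 1.5, within-person SD 1.5, half re-use, log-odds of re-use rising 0.3 or 1.0 per point. Total SD is √(1.0² + 1.5²) = 1.80 with ρ = 1.0²/1.80² = 0.31, or √(1.5² + 1.5²) = 2.12 with ρ = 0.50. Declines are from unrounded values.

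| Between-person SD | Log-odds per point | Odds ratio per SD | M1 | M2 | False decline |
|---|---|---|---|---|---|
| 1.0 | 0.3 | 1.7 | 1.96 | 1.64 | 0.32 |
| 1.0 | 1.0 | 6.1 | 2.55 | 1.82 | 0.72 |
| 1.5 | 0.3 | 1.9 | 2.12 | 1.81 | 0.31 |
| 1.5 | 1.0 | 8.3 | 2.82 | 2.16 | 0.66 |

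The rows with log-odds 1.0 imply very strong dependence; the other two are more credible. An estimate that keeps single-use participants' first episodes returns 1.50.

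**4. The worsening rule alone.** Assume re-use is otherwise random, μ = 1.5, between-person SD 1.25, within-person SD 1.5 (total 1.95, ρ = 0.41), and worsening means a score above onset. The share worsening is Φ(−1.5/1.95) = 22%. If all of them stop, repeat users show 2.24 then 1.81. If half stop, they show 1.83 then 1.63. No preference of satisfied users for re-use is needed.

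**5. The plan's mean 2 and SD 5.** Assume ρ = 0.5 and 60% continuing, about 58 of the 97 treated participants sought in section 5.1.

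| Odds ratio of continuing, per SD | M1 | M2 | False decline | Paired tests finding a change at 5% |
|---|---|---|---|---|
| 1 | 2.00 | 2.00 | 0 | 5% |
| 1.5 | 2.78 | 2.39 | 0.39 | 9% |
| 2 | 3.25 | 2.63 | 0.63 | about 15% |
| 3 | 3.77 | 2.89 | 0.89 | 27% |

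For odds ratios 1.5 to 3, continuation of 40 to 80% and ρ of 0.3 to 0.7, M1 runs from 2.40 to 4.66 and the decline from 0.12 to 1.86. With SD 2.5 the ranges are 2.20 to 3.33 and 0.06 to 0.93. Across odds ratios 1 to 3, a likelihood estimate on all treated participants gives 1.99 to 2.01 at both episodes.

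**6. Other directions.** In the setting of step 5, an odds ratio of 1/1.5 gives 1.22 then 1.61: understatement and a false rise. Selection on headache frequency alone, correlated −0.3, 0 or +0.3 with patient-level benefit, gives 1.32, 2.00 or 2.68 at both episodes, with no decline.

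All these calculations treat change as unbounded and normal, although the scale runs from 0 to 10.

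**The case against.** The strongest reply is that no passage says re-use depends on benefit. Everyone is asked to repeat, everyone receives a three-episode supply and weekly reminders, and the gift card depends on the exit survey and completed forms. Section 7.2 assumes that only half of the enrolled participants will have any headache in 60 days, so frequency must be a large part of who repeats, and step 6 shows that frequency selection alone produces no decline. Adverse-event stopping selects on tolerability, which is not pain relief. All this stands, and it is why the conclusion is worded as likely and possible. It does not remove the worsening rule of section 2.2.3, which acts on the measured outcome.

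A reader might infer that the plan selects people on first-episode benefit, so that inflation and a false decline are certain. The documents do not support this: the dependence is an inference, and its strength and sign are unknown. A reader might also infer that single-use data are discarded or the primary result inflated. They are not discarded: ITT keeps everyone who took the product once, and the restriction does not touch that analysis.

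The size can also be challenged. Step 3 considers only positive dependence, and recovery of 1.50 follows from simulating re-use on recorded data. With 48 repeat users (half of 97), the standard error of the change is about √2 × 1.5/√48 = 0.31, so a decline of 0.3 to 0.7 is one to two standard errors. A false finding is possible in a single trial, not assured.

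Lastly, the analysis is exploratory and its method is deferred. That limits the seriousness, but the restriction itself is already written and a better choice is available.

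**Conclusion.** The concern holds in a conditional form. Restricting the longitudinal analysis to repeat reporters builds in selection related to first-episode outcome, through optional repeats and the stopping advice, together with selection on headache frequency. Estimates from this subset are likely to overstate improvement and may show a spurious decline. Under assumed positive dependence the false decline is about 0.3 to 0.7 points (step 3), or about 0.2 to 0.4 from the worsening rule alone (step 4). These sizes rest on an assumed dependence of re-use, continuation share, variance components and a constant true effect; the documents give none of these for repeat use. This is a recommended change to one hypothesis-generating secondary analysis and no challenge to the primary one.

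**What to change.** Replace the restriction in the SAP with one mixed model on all recorded episodes of all treated participants. Include a participant random effect, episode number, time point, onset score and baseline headache frequency, so that single-use participants contribute their first episode. Because each episode yields three post-dose readings, either fit each time point separately or add an episode-within-participant effect, so that readings from one episode are not treated as independent.

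Add a table of first-episode change for single-use and repeat users side by side. Report the repeat-user subset only descriptively.

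The cost is a few sentences in the SAP and a standard model in R, the software already intended; headache frequency is already on the baseline form. The downside is small: the model assumes that re-use depends only on recorded data, which should be stated as a limitation.

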7.2 Sample Size Considerations

Based on information from a variety of studies, a highly pessimistic assumption is that there would be a mean improvement of 2 points on the Mankoski scale with a standard deviation of 5 points. Based on these assumptions, a sample size of 68 patients would result in a 90% power to detect an improvement using the paired-sample *t*-test. We also assume that 50% of the patients will experience headaches during the 60-day period; the other patients would furnish no useful data. The final sample size of 200 patients has been chosen to allow for various contingencies, including uncertainties in the assumptions and about compliance in this self-reported trial. If data from multiple headaches per patient are useful, the power to detect an improvement would increase.

It should be emphasized that these assumptions are for sample size purposes only. Trial analysis will use the data as collected.

As discussed above, the number 200 may be increased based on observed data concerning the number of participants with heartburn/indigestion. The actual outcomes of treated participants will not be considered in this analysis, merely whether or not enrolled participants have reported starting using the test product. The method of reevaluating the sample size will be described in the Statistical Analysis Plan.

7.3 Analysis Plan

Separate tables will be presented showing the changes from baseline for tension headache severity and functional status at each time point. The changes will be evaluated by the paired-sample t-test. An appropriate nonparametric analysis will also be reported.

Secondary endpoints will be gathered on the subjective experience of these participants related to general health, functional status, personal experience with the products. The secondary endpoints will be self-reported by the participant on their online portal. There will be a questionnaire related to general health, functional status, and the subjective experience of the participant administered at baseline and at study exit.

The purpose of the secondary analyses is to investigate the association between various baseline and other measurements and outcome variables. These secondary analyses are considered hypothesis generating, and the descriptions are somewhat informal. The trial data may suggest secondary analyses not described here.

General statistical methods:

Data will be analyzed using standard statistical methods, as further specified in a statistical analysis plan (SAP), which will be prepared in detail later.

- Data analysis will largely consist of summary statistics and graphs. The only formal group comparisons will be in covariate analyses.
- For continuous variables data presentation will consist of means, confidence intervals computed using the t-statistic, medians, and interquartile ranges. Group comparisons will use t-tests or ANOVA.
- For discrete variables confidence intervals will use the exact intervals, where available.
 Group comparisons will use Fisher's exact test, with the Monte Carlo version used where computationally necessary.
- For time to event variables analysis will use the Kaplan-Meier algorithm, and group comparisons will use the log-rank or proportional hazards methods, depending on the data type.
- Visual analog scale values will be treated as continuous variables. Frequency counts will also be provided for scales with 10 or fewer distinct response levels.
- Covariate analyses will investigate the relation between baseline and outcome variables, using methods appropriate to the data types involved. Age, gender, and baseline medications will be included in these analyses where appropriate data are available.
- Present intention is that the analysis will be performed in R, and the precise form of algorithms will be the default of R. Kaplan-Meier, log-rank, and proportional hazards algorithms will be the defaults of the survival package. [13]
- The exact items to be compared depend on what is reported in each historical control study. When possible, the items will include symptom relief at each time measured, including within-patient p-values, and time to the lowest level on a 4-point scale and to

the lowest 2 levels on a 10-point scale. as well as reported baseline characteristics. When two-arm studies are compared, both arms will be reported in this comparison. Specific studies to be considered will be identified prior to the analysis of actual trial data.

8 Informed Consent Process

The study protocol and informed consent will be reviewed approved by Advarra Institutional Review Board, prior to study start.

Study candidates will learn about the study via digital advertisements. If interested in learning more, they will be referred to a website "landing page" that will provide detailed information about the study. They may opt to complete a screening survey ascertaining study eligibility through patient reported outcomes. If successfully completed (no exclusion criteria are selected), candidate will be invited to review the study consent form tutorial which includes the opportunity to ask questions related to the study from the Principal Investigator or delegated authority of the investigator. Candidate will be provided with contact information to reach investigator or study manager as desired.

Candidate may sign the informed consent via electronic signature as provided by Hawthorne Effect. The study manager will verify candidate signature prior to enrollment as a study participant.

9 Subject Confidentiality

All participants' data and personal information will be kept confidential. Only those involved with the study will have access to participant information. The data will be stored by Hawthorne Effect on a HIPAA compliant platform. The platform, which the data is stored on, will require a personalized username and password to gain access.

10 Publication

Prior to the first patient enrolled, study will be registered on clinicaltrials.gov and submit the results for advertisement and promotion purposes.

11 Limitations

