4.2 Required Behavior

During the 1 hour after taking the test product, no medication or supplementation (including all CBD products) other than the test product should be taken. Once the 1-hour report has been submitted the patient may take other medications.

Patients are asked to limit the consumption of alcohol beverages to less than or equal to two drinks per day and to abstain from the use of cannabis for the duration of the study.

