- **3** Annoying enough to be distracting. Mild painkillers take care of it (Aspirin, Ibuprofen).
- **4** Can be ignored if you are really involved in your work, but still distracting. Mild painkillers remove pain for 3-4 hours.
- **5** Can't be ignored for more than 30 minutes. Mild painkillers ameliorate pain for 3-4 hours.
- **6** Can't be ignored for any length of time, but you can still go to work and participate in social activities. Stronger painkillers (Codeine, narcotics) reduce pain for 3-4 hours.
- **7** Makes it difficult to concentrate, interferes with sleep. You can still function with effort. Stronger painkillers are only partially effective.
- **8** Physical activity severely limited. You can read and converse with effort. Nausea and dizziness set in as factors of pain.
- 9 Unable to speak. Crying out or moaning uncontrollably near delirium.
- 10 Unconscious. Pain makes you pass out.

	Afte	r your	headache	resolved	please com	plete any	of the	following	questions i	if applicabl
--	------	--------	----------	----------	------------	-----------	--------	-----------	-------------	--------------

Did your symptoms resolve completely with the test product? Yes No If yes, time of complete symptom resolution:						
Did you need to take another medication: Yes No						
Medication #1:	Dose:	Time:				
Medication #2:	Dose:	Time:				
Medication #3:	Dose:	Time:				
Did your symptoms resolve completely with taking your medication? Yes No						
After taking medication, time of complete resolution of symptoms:						
Did you experience any side effects after taking the test product? (Y/N) If yes, Please fill out the Adverse Event form.						

13.1.6Appendix F Study Exit Form

symptoms? (y/n)

Study Exit

1.	Pleas	e rate y	our ov	erall ex	perience w	ith th	e test	produc	t.	
0 Poor	1	2	3	4	5 Neutral	6	7	8	9	10 Excellent
1a	. Why?	(free r	espons	e)						
2.	Do yo	ou feel t	hat th	e test p	roduct help	ed w	ith yo	ur head	aches i)
0 Not at	all	2	3	4	5 Neutral	6	7	8	9	10 definitely
3. How likely are you to recommend the test product to your friends or family members?										
0 Not Li	1 kely	2	3	4	5 Neutral	6	7	8	9	10 Extremely Likely
4. Do you feel that the test product helped your body cope with occasional tension and occasional head discomfort?										
0 Not at	all	2	3	4	5 Neutral	6	7	8	9	10 definitely
5.		=	_		you like to sistency, or				-	xperience with the sponse)

6. Did the test product help prevent you from having to take any other medication for your

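### Time to other medication: Kaplan-Meier is planned with no horizon and no rule for resolved headaches, and it overstates use if those episodes are censored at resolution or at 60 minutes

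*Combined protocol and SAP*

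**What the plan says.** The endpoint is defined in Section 7.1: "Time to intervention (taking any product other than the study medication) will be analyzed as a time dependent variable". The same sentence goes on to fix the time origin: "with the clock starting when the test product is taken". I read this as an ordinary time-to-event endpoint. Section 7.3 supplies the method: "For time to event variables analysis will use the Kaplan-Meier algorithm". It adds that "Kaplan-Meier, log-rank, and proportional hazards algorithms will be the defaults of the survival package". Neither section names a competing event, a censoring rule or an end time per episode.

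Section 4.2 sets the rule for the first hour: "no medication or supplementation (including all CBD products) other than the test product should be taken". After that, "Once the 1-hour report has been submitted the patient may take other medications".

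On data capture, Section 6.1 says "Once the participant's symptoms resolve, the participant will complete the headache diary". The diary (Appendix E) asks whether symptoms resolved completely with the test product and then "If yes, time of complete symptom resolution". It also asks whether another medication was needed, with dose and time, and when symptoms resolved after that medication. The schedule in Section 6.2 marks the diary at event start and at 60 minutes.

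Sections 7.1 and 7.3 describe the secondary analyses as informal and hypothesis generating. Section 7.3 leaves detail to an SAP still to be written.

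**The concern.** Kaplan-Meier needs an end time for every episode without the event. For a participant who never took other medication, the diary offers only the 60-minute rating and, in some cases, the time of complete resolution. Censoring at resolution assumes that people whose headache has ended would go on to take other medication at the same rate as those still in pain. They would not, so the censoring is informative, and one minus Kaplan-Meier describes use in a setting where headaches never resolve. Censoring every non-taker at 60 minutes is worse, because only takers then remain in the risk set.

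This is the only planned time-based measure of whether the product spares other medication, and the synopsis says the data may inform a two-arm trial. The error would make the product look worse than it is. Two analysts following the present text could report very different percentages.

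**Working it through.** **No stated figure to reproduce.** The documents give no rate, horizon or power for this endpoint. The only power calculation, 68 patients for the primary paired t-test, reproduces (power 0.902 at an assumed two-sided 0.05) and plays no part here.

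**Inputs.** From the documents: the event and time origin (7.1), the estimator (7.3) and the barred first hour (4.2). Assumed, for illustration: constant hazards after the barred hour, with other medication r = 0.3 per hour and resolution s = 0.3 or 0.6 per hour. T is hours after the barred hour, so T = 2 is three hours after dosing.

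**Formulas, among headaches still present at 60 minutes.**
- Kaplan-Meier with resolution censored: 1 − exp(−rT)
- Share actually taking other medication: r/(r+s) × [1 − exp(−(r+s)T)]

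**Numbers.**
- Kaplan-Meier, T = 2: 1 − exp(−0.6) = 45%. T = 4: 1 − exp(−1.2) = 70%.
- True share, s = 0.6: T = 2, (0.3/0.9) × [1 − exp(−1.8)] = 28%. T = 4, (0.3/0.9) × [1 − exp(−3.6)] = 32%.
- True share, s = 0.3: T = 2, (0.3/0.6) × [1 − exp(−1.2)] = 35%. T = 4, (0.3/0.6) × [1 − exp(−2.4)] = 45%.

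| Hours after the barred hour | 1 − KM | True, s = 0.6 | True, s = 0.3 |
|---|---|---|---|
| 2 | 45% | 28% | 35% |
| 4 | 70% | 32% | 45% |

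**All treated episodes, from dosing.** If resolution also runs at s during the first hour, the true shares are multiplied by exp(−s), which is 0.549 for s = 0.6 and 0.741 for s = 0.3. They become 15% and 26% at T = 2, and 18% and 34% at T = 4. The Kaplan-Meier figures do not change, so the gap widens.

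**Other assumed hazards.** With resolution from dosing at 0.1 to 1.0 per hour and other medication from 60 minutes at 0.1 to 0.5 per hour, the excess four hours after dosing ran from 25.9% against 20.4% (5.5 points) to 77.7% against 12.1% (65.6 points).

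**The alternative handling.** In a simulation of 400,000 episodes (resolution 0.5, other medication 0.25 per hour, 24 hours), keeping resolved episodes event-free in the risk set gave 20.2%, equal to the crude proportion of 20.2%. Censoring at resolution gave about 100%. Resetting the clock at 60 minutes while still censoring at resolution also gave about 100%, against 33.3% of headaches unresolved at 60 minutes.

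**Censoring at the 60-minute report.** If every non-taker leaves at 60 minutes, everyone left in the risk set eventually has the event, so one minus Kaplan-Meier climbs to 100% whatever the true share.

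**Effect of the barred hour.** With other medication at 0.25 per hour, four hours after dosing, one minus Kaplan-Meier is 1 − exp(−0.25 × 4) = 63.2% without the bar and 1 − exp(−0.25 × 3) = 52.8% with it. With resolution at 0.5 per hour, the true share falls from 31.7% to 18.1%. The bar suppresses early events.

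**The case against.** The strongest reply is that no section says resolution is censored. Naming Kaplan-Meier and the R defaults does not settle who is censored when. The diary's yes/no item on other medication lets an analyst record an episode as ended without the event, and carrying it to a common horizon removes the bias. Detail is deferred to the SAP, the endpoint is exploratory, and every hazard above is assumed. The participant insert in Appendix H also breaks off in the available text, so an end time given there cannot be ruled out.

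All of this stands, and it makes the point conditional. It does not remove it: the unbiased handling needs a horizon and a rule that the available text does not state, while the times the form does collect invite the biased one.

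A reader might infer more, in four ways that the documents do not support:
- That the plan itself treats resolution as censoring. It is silent.
- That starting the clock inside the barred hour inflates the estimate. It works in the opposite direction.
- That the schedule confines diary data to the barred hour. Sections 4 and 6.1 and Appendix E have later medication recorded in the diary.
- That this is the main measure of sparing other medication. The exit form also asks whether the product prevented its use.

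**Conclusion.** The point holds in conditional form. Kaplan-Meier from dosing, with no horizon and no handling of resolution, overstates the share of episodes needing other medication if non-takers are censored at resolution or at 60 minutes. With censoring at resolution and the assumed hazards, the excess is about 10 to 17 points two hours after the barred hour (45% against 35% or 28%) and about 25 to 38 points four hours after it (70% against 45% or 32%). These sizes rest on constant hazards chosen for illustration; the direction does not depend on the values chosen. If resolved episodes are kept event-free to a common horizon, there is no overstatement.

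The barred hour is a separate matter of interpretation: before 60 minutes the curve reflects adherence to the rule more than need. The endpoint is secondary and hypothesis generating, and the primary paired comparison and its sample size are untouched.

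**What to change.** In the SAP:

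1. Keep dosing as the origin and keep all treated episodes. Starting the curve at 60 minutes would drop those who resolved early and those who took other medication early.
2. Report the Aalen-Johansen cumulative incidence of other medication, with resolution without other medication as the competing event. The R survival package that the plan names can do this.
3. Equivalently, keep resolved non-takers event-free in the risk set to one stated horizon. The two agree when no episode is lost before the horizon. This form also covers non-takers with no recorded resolution time, since Appendix E asks a non-taker for that time only if symptoms resolved completely with the product.
4. Censor only episodes still unresolved without other medication at that horizon.
5. Mark the first 60 minutes on the curve as the period when other medication is barred, and report use within it as a count of deviations.

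The cost is mainly SAP wording. A horizon has to be chosen and justified, and some resolution times will be missing, so the SAP should say that a non-taker with a completed diary is taken as event-free to the horizon. No change to sample size or the primary analysis is needed.
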